2.6.2.4 Peak Expiratory Flow Rate (PEF)

All the patients are instructed to record PEF twice daily using a mini Peak Flow Meter device, once in the morning (before taking the morning dose) and once approximately 12 h later in the evening (before taking the evening dose), from screening and throughout the study.

PEF (liters/min) will be analyzed separately for morning and evening values. The baseline values are defined as the average from all non-missing records taken over the last 14 days of the run-in period between run-in Visit 101 and up to one day before first dose of study drug. Mean values will be calculated over the first 26 weeks and over the whole 52 weeks of double-blind treatment.

Separate ANCOVA will be performed to investigate treatment differences in the change from baseline in mean morning/evening PEF during the first 26 weeks and during the whole 52 weeks of double-blind treatment. The ANCOVA model will contain treatment, age (12 to 17, or ≥ 18), region as fixed effect factors with center nested within region as a random effect and, baseline morning/evening PEF, FEV₁ prior to inhalation and FEV₁ within 15 to 30 min post inhalation of salbutamol/albuterol (components of SABA reversibility) as covariates. LS means and associated 95% confidence intervals will be presented for treatments and treatment differences.

In addition, the mean morning/evening PEF will be summarized by 4 weekly (28 days) intervals and analyzed using a similar MMRM as specified for the primary analysis with baseline FEV₁ value replaced with the appropriate baseline PEF.

2.6.2.5 Asthma symptom based on e-Diary

Daily e-Diary recordings will be used to derive

- the mean daytime asthma symptom score i.e., the mean score over the 5 evening questions with respect to shortness of breath, wheeze, cough, chest tightness, and 'Did your respiratory symptoms stop you from performing your usual daily activities?', each with scores from 0 (no problems) to 4 (very severe problems)
- the total daily symptom score, defined as the sum of the nighttime score ('How did you sleep last night?' with scores from 0 - 4), the morning awakening score ('Did you have asthma symptoms upon awakening in the morning?' with scores from 0 - 4) and the mean daytime asthma symptom score. The sum will be in the range of 0 – 12.
- day with no daytime symptoms, i.e., all 5 evening questions must have a score = 0
- night with no night-time awakenings, i.e., the question 'How did you sleep last night?' must be answered with 'I did not wake up because of any breathing problems'
- morning with no symptoms on awakening, i.e., the question 'Did you have asthma symptoms upon awakening in the morning?' to be answered with 'None'
- asthma symptoms free days, i.e., days with no daytime symptoms and no night-time awakenings and no symptoms on awakening

The baseline values are defined as the average from all non-missing records taken over the last 14 days of the run-in period between run-in Visit 101 and up to one day before first dose of

study drug. Daily scores will be averaged for each patient over Weeks 1-26, the complete 52 weeks double-blind period, and over 4 weekly intervals (from Weeks 1-4 up to Weeks 49-52). Days with no daytime symptoms, nights with no night-time awakenings, mornings with no symptoms on awakening, and days with no asthma symptoms will be expressed in terms of percentages. The percentages will be calculated as $100 * \text{total number of days without symptoms (daytime, night-time, morning, etc.)} / \text{total number of days in the interval (i.e. 28 days for 4 week interval)}$. The same intervals as used for average scores will be used for analyzing percentage of days. In case of non-convergence or evidence of highly skewed data, non-parametric tests such as Wilcoxon Rank Sum Test will be explored. For post-baseline periods only the days on double-blind treatment will be considered. ANCOVA and MMRM will be performed on changes from baseline similar to the analysis of PEF with baseline PEF value replaced with the appropriate baseline percentage.

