16.1.9.3.2 Baseline measurements

In general, baseline is defined as the last measurement before the first dose of study drug at Day 1.

1) For all **FEV₁, FVC, and FEF₂₅₋₇₅** endpoints, the baseline value is defined as the average of the values taken at -45 and -15 min prior to first dose of study drug at the evening of Day 1. Checks will be performed to ensure both values were indeed taken prior to the first dose of study drug. If one of the -45 and -15 min values is missing (or is not confirmed to be pre-dose) then the remaining non-missing value will be taken as the baseline. If both values are missing (or not confirmed to be pre-dose), then the last out of the pre-bronchodilator measurements taken at the run-in Visits 101 and 102 or at unscheduled run-in visits will be used as the baseline. If the FEV₁, FVC or FEF₂₅₋₇₅ measurements are missing both on Day 1 and at run-in visits, the respective baseline values will be set to missing. Measurements taken within 6 hours of rescue use, and/or within 7 days of systemic corticosteroid use, and/or 3 months of single depot corticosteroid injection, will be set to missing.

For all baseline spirometry measurements, we exclude the implausible values. Specifically, if a patient has implausible FEV₁ value (defined as > 7 L) at baseline assessment, all spirometry measurements related to that assessment will be excluded.

2) For the **ACQ** scores, the baseline value is defined as the score obtained at Day 1 (V102). If the value is missing, the last measurements from run-in visit 101 or unscheduled run-in visits will be used.

3) For patient **diary data (PEF, symptoms, and rescue medication use)**, the baseline values are defined as the average from all non-missing records taken in the run-in period over 14 days from Visit 101 up to one day before first dose of study drug (i.e., from Day -14 to Day -1 inclusively). Missing diary data will not be imputed.

Baseline PEF will be calculated separately for morning and evening values.

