The night-time symptom score consists of one question 'How did you sleep last night?' which has to be answered with scores from 0 = 'I did not wake up because of any breathing problems.' up to 4 = 'I had difficulty sleeping because of my breathing problems even though I used my rescue medication.' The morning score consists of the question 'Did you have asthma symptoms upon awakening in the morning?' which has to be answered with scores from 0 = 'None' up to 4 = 'Very Severe'. There are 5 questions including the today's severity of shortness of breath, wheeze, cough, and chest tightness during the past 12 hours, and 'Did your respiratory symptoms stop you from performing your usual daily activities?' which are part of the daytime symptom score. All have to be answered with a score from 0 = 'None / Not at all' up to 4 = 'Very Severe / Completely'. The average of the 5 scores is defined as the daytime symptom score. The baseline scores will be derived by averaging over the days of the run-in period with non-missing data, separately for each score, the night-time, morning, and daytime symptom score.

The baseline total daily symptom score will be obtained in the first step by adding the night-time symptom score, the morning score, and the mean daytime symptom score for each single day. In the second step, these daily symptom scores will be averaged over the days of the run-in period with non-missing data. The score is in the range from 0 to 12. For the derivation of the total daily symptom score, all 3 scores have to be available at that day. Otherwise a total daily symptom score will not be calculated for that day.

Rescue medication use will be analyzed separately for the number of puffs during daytime, night-time, and over the complete 24 hours. Baseline is defined as the average number of puffs per day in the run-in period. If for the value over the whole day (24 hours) the number of puffs is missing for part of the day (either day-time or night-time) then a half day will be used in the denominator to calculate the average value. Any values > 30 for the number of puffs of rescue medication in a 12 hour period will be set to missing. These high numbers are not realistic and could impact the analyses.

If a patient has less than 7 days with non-missing data, then the respective baseline value will be set to missing.

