For **diary data (PEF, symptom scores and rescue medication use)**, post-baseline measurements start with the morning recordings at Day 2 and end with the evening recordings one day after the last evening dose. Summary data (i.e., mean values and percentage of days with) will be calculated for 4-weekly intervals (defined as 28 days), for Weeks 1 – 26 (defined up to Visit 207, Day 183), and for Weeks 1 – 52 (defined as the whole treatment period up to Visit 214, Day 365). Similar calculations as for baseline diary data will be done. If there will be less than 14 days with data in a 4-week period, then the data should collapse with the previous 4-week period. For Weeks 1 – 26 and 1 – 52, summary values will only be calculated if a patient has at least 30% of their diary days and at least 20 diary days with evaluable data for that variable in the period of interest.

For **safety data**, post-baseline measurements comprise recordings up to the last dose of study drug + 7 days for laboratory, ECG, vital signs, non-serious AE and up to the last dose of study drug + 30 days for SAEs and death. ECG, vital signs and laboratory values which have complete date and time values are assigned to pre or post-dose assessment based on the actual date/time. However, values with missing date/time are assigned to their respective scheduled visit date and time given the visit number and time point are non-missing. If a measurement scheduled as

pre-dose is actually performed post-dose, or vice versa, the data will not be used for by time point assessments but will be included in the summaries of the notable values and extreme values.

When change from baseline is of interest the following formula will be used for each scheduled visit and time-point where baseline and post-baseline values are both available:

Change from baseline = post-baseline value – baseline value.

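### The SAP gives two conflicting denominators for the e-Diary symptom-free percentages, and the one written out counts missed on-treatment entries as days with symptoms

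*SAP*

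**What the plan says.** SAP 2.6.2.5 covers four secondary outcomes, expressed as percentages: days without daytime symptoms, nights without awakening, mornings without symptoms on waking, and days free of all three. The divisor is the "total number of days in the interval (i.e. 28 days for 4 week interval"). The same section adds: "For post-baseline periods only the days on double-blind treatment will be considered".

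For baseline, SAP 2.6.2.5 says: "The baseline values are defined as the average from all non-missing records taken over the last 14 days of the run-in period". SAP 16.1.9.3.2 gives the same rule for all diary data and adds, in that baseline subsection, "Missing diary data will not be imputed". For the total daily symptom score it says that "these daily symptom scores will be averaged over the days of the run-in period with non-missing data".

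For post-baseline diary data, SAP 16.1.9.3.3 names both means and percentages of days and says: "Similar calculations as for baseline diary data will be done". It then sets minimum amounts of data. For 4-week periods: "If there will be less than 14 days with data in a 4-week period, then the data should collapse with the previous 4-week period". A Weeks 1-26 or 1-52 value is calculated only with "at least 30% of their diary days and at least 20 diary days with evaluable data for that variable".

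**The concern.** The numerator in SAP 2.6.2.5 depends on recorded answers: all five evening items must score zero, the sleep item must be answered as not woken, and the awakening item must be answered as none. A day without an entry cannot qualify. If the divisor is every day in the interval, that day counts as symptomatic.

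The baseline rule, which 16.1.9.3.3 appears to carry forward, would drop the missed day from both numerator and denominator. Two programmers working from these two places would therefore get different values for four secondary endpoints. Under the 2.6.2.5 formula the endpoint partly measures diary completion. The composite symptom-free day is the most exposed, because it needs both the morning and the evening entries.

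**Working it through.** The plan states no result to reproduce. The one figure in the formula is right: 4 × 7 = 28 days. The check compares two definitions:

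- A = 100 × symptom-free days / all days in the interval (SAP 2.6.2.5)
- B = 100 × symptom-free days / days with data (the baseline rule)

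**Step 1: how much missing data the SAP allows.** Under SAP 16.1.9.3.3 post-baseline diary data start on Day 2. Weeks 1-26 end on Day 183 and Weeks 1-52 on Day 365.

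- Weeks 1-26: 183 − 2 + 1 = 182 days; 0.30 × 182 = 54.6, so at least 55 days.
- Weeks 1-52: 365 − 2 + 1 = 364 days; 0.30 × 364 = 109.2, so at least 110 days.
- Both exceed the 20-day minimum. An uncollapsed 4-week interval needs 14 days.

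For a patient treated throughout, with the minimum data and symptom-free on every recorded day:

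| Interval | Days with data / all days | A | B |
|---|---|---|---|
| 4 weeks | 14 / 28 | 50.0% | 100% |
| Weeks 1-26 | 55 / 182 | 30.2% | 100% |
| Weeks 1-52 | 110 / 364 | 30.2% | 100% |

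**Step 2: equal completion in both arms.** If a fraction c of entries is completed, unrelated to symptoms, a true rate p becomes c × p under A. The arm difference becomes c × (p1 − p2). For 60% against 50%, the 10-point difference becomes 9 points at c = 0.9, 8 at c = 0.8 and 6 at c = 0.6. Under B it stays at 10.

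**Step 3: unequal completion, no true difference.** A gives p × (c1 − c2). At p = 50%, completion of 90% against 85% gives 50 × 0.05 = 2.5 points; 90% against 80% gives 50 × 0.10 = 5 points. The better-completing arm looks better, whichever arm that is. Under B the difference is 0.

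**Step 4: change within an arm.** With baseline on non-missing records and follow-up on all days, an unchanged 50% rate at 80% completion gives 50 × 0.8 − 50 = −10 points, an apparent worsening.

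**Step 5: entries missed more often on bad days.** Suppose 90% completion on symptom-free days and 70% on other days.

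- True 50%: B = 0.5 × 0.9 / (0.5 × 0.9 + 0.5 × 0.7) = 0.45 / 0.80 = 56.25%; A = 45%.
- True 60%: B = 0.6 × 0.9 / (0.6 × 0.9 + 0.4 × 0.7) = 0.54 / 0.82 = 65.85%; A = 54%.
- Difference between arms (true value 10): B = 9.6 points; A = 9.0 points.

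All completion and symptom rates in Steps 2 to 5 are assumptions.

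**The case against.** The strongest counter-argument concerns the mixed denominators. The models include the baseline value as a covariate, so analysing change from baseline or the post-baseline value gives the same treatment contrast. This is correct. The mismatch between baseline and follow-up does not itself bias the arm comparison, and Step 4 affects only within-arm changes. The attenuation and false difference in Steps 2 and 3 come from the post-baseline denominator alone and remain.

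Second, 16.1.9.3.3 writes out no denominator, and similar calculations could mean only how scores are derived. The sentence on averaging over days with data concerns a score, and the sentence on non-imputation sits under baseline. So that section points to days with data without stating it. However, its minimum-data rules fit that reading, and collapsing a sparse period fits poorly with a fixed 28. If the 2.6.2.5 formula were applied to baseline as well, it would contradict the stated baseline definition.

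Third, days with data is not always closer to the truth. In Step 5, for a true 50%, B is off by 6.25 points and A by 5. For a single arm's level that stands; for the difference between arms, B is closer.

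Fourth, the figures in Step 1 are worst cases for one patient. They take the 30% rule to refer to all days in the period, which the SAP does not spell out. The listed objectives for these percentages are over 52 weeks, so the 4-week and 26-week figures concern additional summaries. Blinding makes a large completion gap less likely, and equal incompleteness only attenuates. All of this limits the size of the problem but does not remove the conflict. Restricting to on-treatment days does not remove it either: that drops days after discontinuation, not entries missed during treatment.

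**Conclusion.** The concern holds. The SAP's explicit formula scores a missed on-treatment entry as symptomatic, its baseline rule does not, and its general rule for post-baseline diary data points to the baseline approach.

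The minimum-data rules bound the effect, but still allow 50% of days to be missing in an uncollapsed 4-week interval and about 70% over 26 or 52 weeks. The effect on arm comparisons depends on completion rates that the documents do not give. At the assumed rates it runs from a 1-point loss on a true 10-point difference (90% completion) to a 4-point loss (60%), with false differences of 2.5 to 5 points for completion gaps of 5 to 10 points at a 50% symptom-free rate.

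The four endpoints are tested at nominal 0.05 outside the controlled family (SAP 2.6.1.3), so the primary and key secondary conclusions are untouched. This should be fixed before the derivations are programmed.

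**What to change.** In SAP 2.6.2.5, make the denominator the number of days (nights, mornings) on double-blind treatment with evaluable diary data for that item in the interval, and state the same rule in 16.1.9.3.3. Keep the 14-day, 30% and 20-day rules. State which denominator a collapsed period takes, since the SAP does not say. Report diary completion by arm.

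The change to the denominator is one SAP sentence and one line of derivation code. Percentages for poor completers will rest on fewer days, and the new denominator assumes that missing entries are unrelated to symptoms. The completion table would help show whether that matters.

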2.6.2.6 Rescue medication

The number of puffs of rescue medication during the past 12 hours is recorded twice (morning/evening) by the patient in the e-Diary. The baseline values are defined as the average from all non-missing records taken over the last 14 days of the run-in period between run-in Visit 101 and up to one day before first dose of study drug.

The mean daily number of puffs of rescue medication use will be calculated for each patient over the first 26 weeks, over the whole 52 weeks of double-blind treatment, and over 4 weekly intervals as described for other data of the e-Diary. This will be done separately for morning (night-time), evening (daytime), and daily (night-time plus daytime) rescue medication use. Similar ANCOVA and MMRM as used for the analysis of PEF with baseline PEF value replaced with the appropriate baseline mean number of puffs.

The percentage of 'rescue medication free days' (defined as any day where the patient did not use any puffs of rescue medication during daytime and night-time) will be summarized by treatment and analyzed in the same way as described for the number of puffs of rescue medication use with baseline mean number of puffs replaced with the baseline percentage of rescue medication free days as a covariate. In case of non-convergence or evidence of highly skewed data, non-parametric tests such as Wilcoxon Rank Sum Test will be explored.

2.6.2.7 Asthma exacerbations

All analyses will base on data as reported on the "Asthma Exacerbation Episodes" eCRF.

In patients with multiple exacerbations, if the start date of an exacerbation was less than 7 days after the end date of a previous episode, then this will be assumed to be one continuous exacerbation with the start date taken from the first episode and the end date from the second or last episode. The worst severity of these episodes will be taken as the severity of the collapsed exacerbation. Collapsing of exacerbation episodes will only be done for efficacy analyses but not for safety analyses of adverse events which includes asthma exacerbations.

Asthma exacerbations starting after the first dose and not later than one day after the date of last dose will be included in the analyses of efficacy.

The following asthma exacerbation-related parameters will be summarized considering the whole 52 weeks of double-blind treatment. The analysis will be performed by exacerbation

category wherever specified. The exacerbation categories are: All (mild, moderate, severe), the combination of moderate or severe, and severe.

The annual rate of asthma exacerbations, by exacerbation category

The (annual) rate of asthma exacerbations will be analyzed using a generalized linear model assuming the negative binomial distribution including treatment, age (12 to 17, ≥ 18 years), region and history of asthma exacerbation in the 12 months prior to screening (Yes, No) as fixed-effect factors, and FEV₁ prior to inhalation and FEV₁ 15 to 30 min post inhalation of salbutamol/albuterol (components of SABA reversibility) as covariates. The log exposure in years will be used as an offset variable in the model (see Section 2.4.1 for the definition of exposure). The estimated rate ratio along with two-sided 95% interval and corresponding p-value will be provided.

Time to first asthma exacerbation, by exacerbation category

Time-to-event variables will be analyzed using a Cox regression model stratified by age (12 to 17, ≥ 18 years). The model will include treatment, region and history of asthma exacerbation in the 12 months prior to screening (Yes, No) as fixed-effect factors, and FEV₁ prior to inhalation and FEV₁ 15 to 30 min post inhalation of salbutamol/albuterol (components of SABA reversibility) as covariates. For treatment comparisons the estimated adjusted hazard ratio will be displayed along with the associated two-sided 95% confidence interval and corresponding p-value. Kaplan-Meier analysis stratified by treatment group will be also presented and displayed graphically. Patients without an event will be considered as censored at the earliest date of (last treatment + 1, death, last visit). In the interim analysis, patients without an event who are ongoing at the time of interim database freeze will be censored at the DLP. For patients having an event, the start date of the exacerbation will be considered to calculate the time to event (i.e., the number of days from start of treatment up to the event start date).

Time to first hospitalization for asthma exacerbation (only for severe exacerbations possible)

The analysis is similar to time to first asthma exacerbation.

Time to permanent discontinuation of study drug due to asthma exacerbation

The analysis is similar to time to first asthma exacerbation.

Duration of asthma exacerbations in days, by exacerbation category

The duration of asthma exacerbations is defined as the sum of days per patient over all exacerbations and the respective lengths (from start to end date). This will be analyzed for treatment group differences using the van Elteren test stratified for age (12 to 17, or ≥ 18), region and history of asthma exacerbation in the 12 months prior to screening (Yes, No).

Total amounts (in doses) of oral corticosteroids used to treat asthma exacerbations

Total amount (in prednisone-equivalent mg doses) of oral corticosteroid used to treat asthma exacerbations during the 52 week treatment period will be summarized descriptively by treatment group.

To estimate the add-on effect of indacaterol (QAB149) to existing MF treatment (in terms of exacerbations), the average difference between QMF149 and MF will be computed for all inferential analyses mentioned above. This difference is interpreted as an average of adding indacaterol to MF, under the assumption that indacaterol effect is not altered by dose of MF. To compute the difference, the QMF149 and MF doses will be pooled by averaging the following contrasts within the specified analyses:

- QMF149 (150/160 µg) vs. MF 400 µg
- QMF149 (150/320 µg) vs. MF 800 µg.

